## **9. OBJECTIVES AND GOALS OF THE STUDY**

### *Primary objective:*

## **Development and validation of a health behaviour theory-based questionnaire to explore the willingness of older adults and informal caregivers to deprescribe (HBQtD)**

To develop and validate a health behavior theory-based questionnaire to examine the older adults' and informal caregivers' determinants of deprescribing intention or behavior (with separate version for older adult and informal caregiver).

### *Secondary objectives:*

- Establish the face and content validity of the questionnaire;
- Assess the psychometric properties of this new tool, by performing an exploratory factor analysis (EFA).

### *Expected benefits of the research*

Despite the many benefits of taking medication, multimorbidity and the chronicity of certain health problems lead to multi-medication intake, which can entail major risks for the older people. Thus, deprescribing is an important dimension in the care of the older adults, and this study intends to provide a new instrument, developed on the basis of constructs from behavioral health theories, which is expected to be more accurate than those currently in use. This tool will thus be able to provide more information about the older adults' and their caregivers' views about deprescribing and also the socio-cognitive factors that can impact their willingness to engage in deprescribing behavior. Consequently, this information could be useful in the development of interventions aimed at medication deprescribing, with a patient-centered or family-centered deprescribing approach.

## **STUDY DESIGN AND METHODOLOGY APPLIED**

### 9.1. Design

#### *Type of study*

Questionnaire development and validation – older adult and informal caregiver version

#### *Study configuration*

The initial questionnaire was developed considering the results of a previous systematic review (article currently being written), which was intended to identify (concepts included in) behavioral health theories (HBTs) that explain older adults' and informal caregivers' deprescribing intention and/or their actual deprescribing behavior. This systematic review, revealed several main dimensions, such as goals intention to deprescribe, perceived risks about medication, self-efficacy towards deprescribing, subjective norms, social support to deprescribe, and finally opportunities for deprescribing. This systematic review, also showed that attitudes was already widely investigated, indeed four systematic reviews and two meta-analysis were already performed, synthesizing studies that have used PATD and the revised version (Seewoodharry et al., 2022; Oktora et al., 2022; Chock et al., 2021; Weir et al., 2021). As a result, the items of this initial questionnaire were developed according to the dimensions found in the systematic review, the main results of the systematic review focused on the rPATD and the Beliefs about Medicines questionnaire (BMQ), since a predictor of risk perception was beliefs about medication (Martin et al., 2013).

The initial version for informal caregivers was developed by modifying the wording of the items, in the version for the older adults, adapting them for informal caregivers.

## **Development and validation of a health behaviour theory-based questionnaire to explore the willingness of older adults and informal caregivers to deprescribe (HBQtD)**

Another two questionnaires will be used in this study: one that measure health literacy (HLS19\_Q12; (Pelikan et al., 2022)) and another one that assess the locus of control (MHLC; (Wallston et al., 1978)). The previous systematic review revealed that the HL was positively associated with the willingness to deprescribe (Gillespie et al., 2019). The HLS19\_Q12 is thus the questionnaire that will be used in this study. This instrument was built on the conceptual framework and definition of comprehensive, general HL developed in the HLS\_EU (Pelikan et al., 2022). Indeed, the concept-based in the development of HLS\_EU refers to “... *people’s knowledge, motivation, and competencies to access, understand, appraise and apply information to form judgements and take decisions in terms of healthcare, disease prevention and health promotion to improve quality of life during the life course*” (Sørensen K et al., 2012 cit by (Pelikan et al., 2022)).

In addition, the locus of control was also identified in one study, in the previous systematic review, as having an impact on deprescribing behavior (Elsesser & Sartory, 1998). As a result, the Multidimensional Health locus of control scale (MHLC; (Wallston et al., 1978)) will be used. According to Lachman (1986) the multidimensional measurement is desirable for the older people, because “*it allows for the possibility of differential change trajectories across dimensions*” (Gurin & Brim, 1984 cit by Lachman, 1986), as in the aging process older people may become more sensitive to the external power or chance, but without changing one’s sense of internal control (Lachman, 1986).

### *Study design*

The development and validation of the questionnaire comprise 4 steps:

#### **1. Item Development process**

The conceptualization of the concepts used in the questionnaire was based on the results of the systematic review carried out previously. The items were built in relation to the most relevant constructs and predictors identified in the results of the systematic review, and some items from two different questionnaires (rPATD and BMQ) were also used to assess the components of some constructs, such as attitudes and perceived risk. The dimensions importance, in a first step were identified by discussion with the promotor in relation to the systematic review results. The questionnaire and items format were also discussed with the promotor, and a statistician from SMCS.

Some considerations have been taken into account in the item construction: “*Statements should be simple and short as possible, and the language used should be familiar to target respondents... Items should address only a single issue... Leading questions should be avoided, as they may bias responses. Items that all respondents would answer similarly should not be used, as they will generate little variance*” (Hinkin, 1998). In addition, items related to deprescribing behavior were regrouped and separated from those related to medication use.

#### **2. Preliminary pilot testing**

All piloting process will follow an iterative approach, allowing adjustments to be made throughout the exchanges between the various stakeholders involved in this process.

a. Prior to the pre-test, the questionnaire will be distributed to 5 colleagues on the research team to check all the initial items and adjust them, if necessary.

b. Then, “cognitive pre-test” will be performed with 5 older adults and 5 informal caregivers to check the linguistic and analytical construction of the items, through respondent

## **Development and validation of a health behaviour theory-based questionnaire to explore the willingness of older adults and informal caregivers to deprescribe (HBQtD)**

understanding of the items in the questionnaire. This first test will be performed by qualitative methodology, more precisely structured interviews. Respondents will be encouraged to express their thinking aloud when answering each item. After this first test, items that caused comprehension problems will be discussed with the research team and then they will be adjusted or eliminated. The results of this first test lead to a first draft of the questionnaire to the older adults and to the informal caregivers.

c. In the following step, the item development and questionnaire validation will include a first round with healthcare professionals, and a second round with older adults and informal caregivers. This phase will assess the face and content validity. Different techniques can be used to assess content validity, but in this study we will use the one proposed by Lawshe (1975), the Content validity ratio (CVR), once it has also been used in other studies such as for the validation of the rPATD (E. Reeve et al., 2016).

### **i. Healthcare professionals**

According to the principle of purposive sampling, 8 health professionals: 2 geriatricians, 2 general practitioners (GP), 2 pharmacists, and 2 nurses, will be enrolled in this study to rate on a Likert-scale the appropriateness of having each item in the questionnaire.

For improving the questionnaire, participants will also be encouraged to make comments and suggestions.

One focus group (FG) will be then organized to discuss the results from this second test, and a second draft can be developed, after discussing the results with the research team and before offering it to older adults and their informal caregivers.

As regards the FG, it's essentially a small group of people, between 6 and 16, who come together to discuss a particular and common subject (Kohn & Christiaens, 2012). Consequently, one group with health care professionals will be composed of at least 6 participants who have showed an interest in participating in the discussion (question at the end of the questionnaire). The focus group will be moderated by the co-investigator and will take place at a location to be agreed with the participants.

### **ii. Older adults and informal caregivers**

As for the healthcare professionals, a convenience sample of 10 older adults, and 10 informal caregivers, will be asked to provide individual feedback on the questionnaire items. One FG, with older adults and informal caregivers will be organized to discuss the results of the self-administered questionnaire. The group will be composed of at least 6 participants (3 older adults and 3 informal caregivers) who have shown an interest in participating in the discussion (question at the end of the questionnaire). A third version of the questionnaire will be obtained after discussion the results with research team.

## **3. Pre-test of the questionnaire – older adult and informal caregiver version**

Once the final version of the questionnaire developed, it will be administered to a small group of participants, generally 10% of the sample size required to perform an EFA (Aithal & Aithal, 2020). It will be asked to the older adults and to the informal caregivers to complete the questionnaire and to provide any comments about the way items have been written and on items comprehension. This pilot study will help to assess the clarity of the items and to remove irrelevant items.

In this validation step will also be administered the HLS19\_Q12 and MHLCS.

**Development and validation of a health behaviour theory-based questionnaire to explore the willingness of older adults and informal caregivers to deprescribe (HBQtD)**

**4. Validation of the questionnaire – older adult and informal caregiver version**

The final item selection process will incorporate the results of the different qualitative analyses (interviews and FG) and quantitative analyses of the field trial data. This final version of the questionnaire will be then applied to a large sample size of older adults and informal caregiver for reliability validation.

This validity process “... refers to the degree to which evidence and theory support the interpretations of test scores for proposed uses of a test. Validity is, therefore, the most fundamental consideration in developing and evaluating tests” (AERA, APA, & NCME, 2014 cit by Clark & Watson, 2019). As a result, during this phase, a construct validity will be carried out, which is related to the “evaluation of the extent to which a measure assesses the construct it is deemed to measure” (Strauss & Smith, 2009). The internal consistency will be also calculated, as it reflects “the extent to which the questionnaire items are inter-correlated, or whether they are consistent in measurement of the same construct” (Tsang et al., 2017). Finally, a test-retest reliability will be performed, by repeating the administration of the same questionnaire with a small sample of participants (20 older adults and 20 informal caregivers) who have already completed the questionnaire. This process will ensure the consistency of questionnaire items responses across repeated administration (Tsang et al., 2017).

The two additional questionnaires (HLS19\_Q12 and MHLCS) will be administered to all participants (older adults and informal caregivers) in this final stage of the questionnaire validation process.

*Expected duration of subject participation*

Participants will be included throughout the questionnaire development and validation process, which will begin as soon as the ethics committee's opinion is received, and will continue until the sample size required for validation of the questionnaire is reached, in the final phase. The whole process is expected to take around 12 months.

*Planned timetable*

Activities/ Months	2023										2024						
	06	07	08	09	10	11	12	01	02	03	04	05	06	07			
Questionnaire development				15d	15d	15d	15d	15d	15d								
Ethics committee																	
Cognitive pre-test with OA and IC																	
Round with HCP																	
FG with HCP																	
Round with OA and IC																	
FG with OA and IC																	
Questionnaire validation																	

HCP: Healthcare professionals; FG: focus group; OA: older adults; IC: informal caregivers

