## **Development and validation of a health behaviour theory-based questionnaire to explore the willingness of older adults and informal caregivers to deprescribe (HBQtD)**

collaborative work between the patient, or even the caregivers, and the health professionals, to achieve the best health outcomes for the patient (Parker et al., 2022; E. Reeve et al., 2013).

In reality, HBT provides a series of concepts deriving from social, cognitive and motivational psychology, that can be useful in understanding why people behave in certain ways in relation to their health (Gehlert & Ward, 2019). The most well-known and often-used theories are the Health belief Model (HBM; (Godin, 1991), the Theory of Planned Behavior (TPB; (Ajzen, 1991), as an extension of the Theory of Reasoned Action (TRA; (Ajzen & Madden, 1986), and the Protection Motivation theory (PMT; (Rogers, 1975). One major limitation of these models is that they actually "predict" behavioral intention, but they do not inform how to change health behaviors (Parker et al., 2022; Bandura, 2004, Godin, 1991).

Consequently, Bandura (2004) proposes a causal model, the Social Cognitive Theory (SCT), that *“offers both predictors and principles on how inform, enable, guide, and motivate people to adapt habits that promote health and reduce those that impair it”*. According to this theory, *“behavior, cognitive and other personal factors, and environmental events all operate as interacting determinants that influences each other bidirectionally”* (Bandura, 1988).

Moreover, given that behavior change involves processes that take place over time, the Trans-Theoretical Model of change (TTM; (Prochaska & DiClemente, 1983)) posits that health behavior change is a process that involves progression through a series of six stages of change: precontemplation, contemplation, preparation, action, maintenance, and termination (Prochaska & Velicer, 1997).

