## **Development and validation of a health behaviour theory-based questionnaire to explore the willingness of older adults and informal caregivers to deprescribe (HBQtD)**

### *Method for data collection*

The questionnaire begins with a short introduction covering the importance of the study, its objectives, anonymity and the non-obligation to participate in the study and withdraw if desired. Consent will be signed before starting to fill in the questionnaire. The questionnaire initially asks 3 questions to determine participant eligibility, and the initial draft of the questionnaire consists of 3 main parts:

1. First section with questions relating to the socio-demographic and clinical characteristics of the participants. There are 5 basic demographic questions related to age, sex, education, relationship status, residence (at home, NH, ...). Three additional questions are included in this section to: (1) assess how the person feels about his or her health or that of the care recipient, on a Likert scale ranging from 1 “Poor” to 5 “Excellent”; (2) to know how many different medications (including those not prescribed by the doctor) the older person/care recipient takes per day; (3) to know if the person or the care recipient has ever tried, in the past, to reduce or stop some of the drugs in their usual treatment; (4) to know if the person/ informal caregiver are willing to deprescribe; (5) to know if the person/ care recipient is currently in the process of deprescribing at least one of the medication he or she is currently taking.
2. Second section with 58 questions for older adult questionnaire version and 55 questions for the informal caregiver version on factors that may be potential obstacles or facilitators to deprescribing behavior. Each item is rate on a Likert scale going from 1 “strongly disagree” to 5 “strongly agree”.

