#### *Sample Size*

According to Yong & Pearce (2013), EFA performs better with a larger sample size, as it reduces the error in the data. However, no formal sample size calculation is available for EFA, some authors recommend at least 200 participants (McCoach et al., 2013), while others put the targeted figure at 300 (Yong & Pearce, 2013). So, in this study, we are targeting a sample of 300 older adults and 300 informal caregivers. For the test-retest reliability, a sample size of 20

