## **Development and validation of a health behaviour theory-based questionnaire to explore the willingness of older adults and informal caregivers to deprescribe (HBQtD)**

older adults, and 20 informal caregivers will be selected, as was used for rPATD validation (E. Reeve et al., 2016) and rPATD version for BZD (Péteïn et al., 2023).

As described earlier, this study will include an heterogeneous sample (recruitment will be carried out in various structures in Brussels and Wallonia ) to minimize the influence of variance and factor loading, which “give us an idea about how much the variable has contributed to the factor... they represent the strength of the correlation between the variable and the factor” (Kline, 1994 cit by Yong & Pearce, 2013).

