### *Psychometric proprieties of the questionnaire*

The appropriateness of the data factor analysis, considered “to be a variable describing how much an individual would score on a factor” (Yong & Pearce, 2013), will be assessed using the Kaiser-Meyers-Olkin test and Bartlett’s test of sphericity. Factors will be extracted using the Principal Axis Factoring, that is based on the notion “that all variables belong to the first group and when the factor is extracted, a residual matrix is calculated. Factors are then extracted successively until there is a large enough of variance accounted for in the correlation matrix” (Tucker & MacCallum, 1997 cit by Yong & Pearce, 2013). In addition, for a better interpretation of the factors, a rotation will be performed, more precisely an oblique rotation (Yong & Pearce, 2013). The number of factors to be retained will be determined using the Kaiser-Guttman criterion (retaining all factors that are above the eigenvalue of 1) and the scree test (retaining all factors that are above the point of inflexion in the scree plot). Loadings above 0.30 will be considered as significant, as “anything lower would suggest a really weak relationship between the variables” (Tabachnic & Fidell, 2007 cit by Yong & Pearce, 2013).

Another essential step in the creation of a questionnaire is to gather evidence of the score's reliability (E. Reeve et al., 2016). In reality, score reliability “is an indication of the consistency, stability, or precision of scores” (McCoach et al., 2013). Consequently, reliability focus on two types of measurement: internal consistency that estimate a “measurement error within the set of questions” (McCoach et al., 2013) and test-retest reliability estimates, that is a measurement error across two or more instrument administration (McCoach et al., 2013).

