The most commonly used estimated of internal consistency is Cronbach’s coefficient alpha ( $\alpha$ ; (McCoach et al., 2013)). Nevertheless,  $\alpha$  is predicted on several assumptions, that are not always respected (Trizano-Hermosilla & Alvarado, 2016; McCoach et al., 2013), which is why the omega coefficient ( $\omega$ ; (McDonald, 1999)) will also be used, as an alternative to  $\alpha$  (Doval, 2023; Trizano-Hermosilla & Alvarado, 2016). In reality, a number of researchers showed that  $\omega$  is a more sensible index, with lower risk of over- or underestimating reliability (Dunn et al., 2014). Therefore, the reliability coefficient range between 0 and 1, and a value above 0.7 will be considered as good internal consistency, while a value above 0.90 will be considered as excellent (Koo & Li, 2016).

According to Koo & Li (2016) “A more desirable measure of reliability should reflect both degree of correlation and agreement between measurements”, that’s why the intraclass correlation coefficient (ICC) will be used to evaluate test-retest reliability at the factor level, and linear-weighted Cohen’s Kappa and percent agreement at the individual item level. These measurements have been used to validate other instruments such as rPATD (E. Reeve et al., 2016) and the rPATD version for BZDs (Péteïn et al., 2023). The ICC classified the reliability

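### The test-retest step sets no interval and no stability check, so its ICC and kappa cannot separate an unstable questionnaire from real change or from recall

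*Combined protocol and SAP*

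**What the plan says.** Section 9.1, step 4 (Validation of the questionnaire) says the retest is done "by repeating the administration of the same questionnaire with a small sample of participants (20 older adults and 20 informal caregivers", drawn from those "who have already completed the questionnaire". No other condition of entry is given.

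Section 9.10.2, Sample Size, repeats the number: "For the test-retest reliability, a sample size of 20" "older adults, and 20 informal caregivers will be selected, as was used for rPATD validation". Two earlier validations are cited there for the sample size only; no interval is taken over from them.

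Section 9.10.2, on psychometric properties, describes test-retest reliability as an estimate "that is a measurement error across two or more instrument administration". It then says that "the intraclass correlation coefficient (ICC) will be used to evaluate test-retest reliability at the factor level", with linear-weighted kappa and percent agreement for single items. The ICC is graded poor below 0.50, moderate from 0.50 to 0.75, good from 0.75 to 0.90 and excellent above 0.90. Whether the ICC is the agreement or the consistency form is not stated.

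The only duration near the retest is about 12 months for the whole process, which is not a retest window. Section 9.1, Method for data collection, shows that the form records the number of medications, self-rated health, and whether the older person or "care recipient is currently in the process of deprescribing at least one of the medication he or she is currently taking". Section 9.5 does not exclude people who are deprescribing. No analysis rule uses these answers for the retest.

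**The concern.** A test-retest coefficient measures reliability only if the true state of the respondents is the same on both occasions and the second answers are not copied from memory. The plan secures neither. A respondent who starts or stops a deprescribing attempt between the two forms may give different answers for a good reason, and the plan books that difference as error. A respondent who receives the second form after a very short time may repeat remembered answers, and the plan books that as reliability.

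At stake is the reading of one of the validation methods named in the synopsis. A sound factor could be graded down or a weak one graded up, and nothing in the analysis would show which had happened. An uncontrolled interval cannot be repaired afterwards, and the change question has to be on the second form before it is sent.

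**Working it through.** **Plan's own figure.** The 20 per group rests on precedent. No target ICC, precision or power is given for it, so there is nothing to reproduce.

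**Model for true change.** First score Y1 = T + e1; second score Y2 = T + D + e2. Total variance at the first form is 1, and R is the reliability in stable people. D equals d (in SD of the score) for a share p of respondents and 0 for the rest, independent of T. Then

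- agreement ICC = 2R / (2 + var(D) + mean(D)²) = 2R / (2 + p·d²)
- consistency ICC = 2R / (2 + var(D)), with var(D) = p(1 − p)d² when all shifts go the same way.

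The documents give neither p nor d, so both are assumptions, as is R = 0.80.

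**Agreement ICC at R = 0.80.**

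- p = 15%, d = 0.5: 1.6 / 2.0375 = 0.785
- p = 10%, d = 1: 1.6 / 2.10 = 0.762
- p = 15%, d = 1: 1.6 / 2.15 = 0.744
- p = 20%, d = 1: 1.6 / 2.20 = 0.727
- p = 15%, d = 1.5: 1.6 / 2.3375 = 0.684

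**Where the plan's 0.75 line is crossed.** Setting 1.6 / (2 + p·d²) = 0.75 gives p·d² = 1.6/0.75 − 2 = 0.133. That is about 13% of respondents at 1 SD (between 2 and 3 of 20), but about 53% at 0.5 SD.

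**Form of the ICC.** At p = 15%, d = 1, the consistency ICC is 1.6 / (2 + 0.1275) = 0.752, against 0.744 for agreement: the two fall on opposite sides of the line. If everyone shifted by 0.5 SD, the consistency form would stay at 0.80 and the agreement form would fall to 1.6 / 2.25 = 0.711.

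**Kappa.** For a five-category item with R = 0.80 (simulated, cut points at ±0.4 and ±1.2), linear-weighted kappa is 0.56 with no change. It is 0.54 with 20% shifting by 0.5 SD and 0.50 with 20% shifting by 1 SD.

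**Chance that changers are present.** 1 − (1 − p)^20 is 64%, 88% and 99% for p = 5%, 10% and 20%.

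**Recall.** If the errors on the two forms correlate at r, the expected ICC is R + r(1 − R). With R = 0.70 and r = 0.4 (both assumed) this is 0.70 + 0.12 = 0.82, so a moderate factor would be graded good.

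**Sampling error for scale.** For an observed ICC of 0.80 with 20 pairs, F = 1.8/0.2 = 9 and the 97.5% point of F(19, 19) is 2.53. The limits are (9/2.53 − 1)/(9/2.53 + 1) = 0.56 and (9 × 2.53 − 1)/(9 × 2.53 + 1) = 0.92. In simulated studies of 20 pairs with true ICC 0.80, 31% fall below 0.75 with nobody changed. This becomes 36% if 3 of 20 shift by 0.5 SD, 52% if 3 shift by 1 SD, and 61% if 4 shift by 1 SD.

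**The case against.** A reader might infer that the omission biases the ICC and kappa downward. The documents do not support that. True change unrelated to the starting score lowers them, but recall raises them, and change positively related to the starting score could offset the fall. Without an interval the net direction cannot be stated.

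A reader might also infer that the protocol itself says intention, self-efficacy, perceived risk and social support move between forms. The sentence in section 7, "given that behavior change involves processes that take place over time", introduces a stage model of behaviour change and says nothing about these constructs over a retest interval. That GPs or pharmacists might prompt a medication change after handing over a form is plausible, but section 9.3 describes only the handing over.

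On size, the defence is largely right. A 0.5 SD shift in a few people hardly matters, and most of the shifts above are smaller than the sampling error with 20 pairs. That does not remove the point: a confidence interval does not show this bias, and more pairs would not shrink it.

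On consequence, the ICC bands are descriptive. No item removal or acceptance rule depends on them, and the 300 per group is set for the factor analysis. This stands and limits the severity.

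Finally, the consent form and appended questionnaires were not available and the timetables are broken in the text, so an interval may be stated there. It would still belong in sections 9.1 and 9.10.2, which give none.

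**Conclusion.** The gap is confirmed: no retest interval, no stability condition, and no use of the status answers that a repeated form would record. As planned, the ICC and kappa cannot be read as questionnaire reliability alone, because instability, true change and recall are pooled.

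The effect is negligible if changes are few or small. It reaches the boundary between moderate and good if roughly 13% or more of respondents shift by 1 SD, given a stable-respondent ICC of 0.80, change unrelated to baseline, and the agreement form. None of these inputs comes from the documents. This is a cheap improvement of modest severity, not a defect in the validation as a whole.

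**What to change.** In section 9.1, step 4, and section 9.10.2:

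1. State one retest window with a minimum and a maximum, chosen and justified by the sponsor.
2. Add one question to the second form: has medication or health changed since the first form?
3. Compute the main ICC and kappa in respondents who report no change and whose current deprescribing status and medication count agree on both forms. Report all-respondent values beside them.
4. Name the ICC form (agreement or consistency).

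Do not define stability by identical answers on willingness or past attempts. Willingness is close to what the tool is meant to explain, and a past attempt cannot truly go from yes to no, so such filters remove response error that the retest should detect. In a simulation with nobody truly changed, 50% willing and assumed links between willingness and the score, filtering on willingness lifted a true ICC of 0.70 to 0.75–0.78 and lost 29 to 33% of pairs. Weaker links would lift it less. With 86% willing, the figure cited in section 7, the ICC barely moved (0.69–0.70), but 16 to 18% of pairs were still lost.

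The cost is protocol wording and one question. A few of the 20 pairs per group leave the main estimate. With 17 pairs, the interval around an ICC of 0.80 widens from 0.56–0.92 to about 0.53–0.92 (same formula, F point 2.76). Retesting a few more of the 300 completers per group would offset this.
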